### SUMMARY of the clinical study

Protocol Number	ILH297-C003
Objective(s):	To evaluate effectiveness and safety of the AcrySof IQ PanOptix Intraocular Lens (IOL) Model TFNT00 when implanted to replace the natural lens following cataract removal.
Trial Population:	Japanese subjects with bilateral cataract aged 20 or over
Trial Design:	Multi-center, Non-control, Open-label
Test Article:	AcrySof® IQ PanOptix™ IOL Model TFNT00
Variable(s):	
Effectiveness:
 
Primary Effectiveness
 
 
- Monocular photopic best corrected distance visual acuity (5 m)
 
- Monocular photopic distance corrected intermediate visual acuity (60 cm)
 
- Monocular photopic distance corrected near visual acuity (40 cm)
 
 
Safety:	
Adverse Events
 
Secondary Surgical Intervention related to optical properties
 
Device Deficiencies
 
Fundus visualization
 
Intraocular Pressure
 
Slit Lamp Examination
 
Dilated Fundus Examination
 
IOL Observations
 
Subjective Posterior Capsule Opacification
 
Posterior Capsulotomy
 
Lens decentration and tilt
  
Laser Flare meter
 
Subjective symptoms
 
Problems during surgery

Usage	The investigational lens will be placed within the capsular bag after removal of the natural crystalline lens following phacoemulsification.
Eye examinations schedule	
Visit 0 : Pre ope
 
Visit 00/00A : Ope (00: 1st eye, 00A: 2nd eye)
 
Visit 1/1A : 1-2 days after implantation (1: 1st eye, 1A: 2nd eye)
 
Visit 2/2A : 7-14 days after implantation (2: 1st eye, 2A: 2nd eye)
 
Visit 3/3A : 30-60 days after implantation (3: 1st eye, 3A: 2nd eye)
 
Visit 4A : 120-180 days after 2nd eye implantation

No. of Subjects:	60 subjects 120 eyes
Anticipated study period	01-Apr-2017 ~ 30-Jun-2018
Medical Monitor	Alcon Japan Ltd.
Sponsor	Alcon Japan Ltd.
GCP compliance:	This clinical study is subject to the Good Clinical Practice for Medical Devices (GCP for Medical Devices) (MHLW Notification No.36 dated March, 2005.)

## 1. INTRODUCTION

### (1) History of development

The first clinical results of the multifocal intraocular lenses were reported in the United States in 1987. The first Japanese clinical study was performed and reported in the early 1990's . In general, multifocal intraocular lenses are roughly divided into diffractive and refractive types. Diffractive lenses are structured to separate incident light energy to far and near visions, while refractive lenses have an optical zone structure consisting of far and near vision zones arranged in an alternate, concentric manner . Since the diffractive multifocal intraocular lens product, "Alcon® AcrySof® ReSTOR® Single Piece" (medical device approval number: 21900BZX00605000, Alcon Japan Ltd.) was first approved in 2007, various multifocal intraocular lenses have been developed in Japan. As opposed to monofocal intraocular lenses, intraocular lenses with 2 or more focuses are collectively called multifocal intraocular lenses. Actually, however, bifocal intraocular lenses focusing on far and intermediate or near objects account for most of multifocal intraocular lenses: all the multifocal intraocular lenses approved in Japan are bifocal. Bifocal intraocular lenses have become popular because they correct an intermediate (1 m to 50 cm) or near vision sacrificed in monofocal intraocular lenses and therefore reduce the dependence on corrective devices including eyeglasses. However, bifocal intraocular lenses may not make the patient satisfy enough because they are designed to focus on distant and near or intermediate visions.

Recently, three trifocal intraocular lenses focusing on far, intermediate, and near objects were released in Europe. All the commercially available trifocal intraocular lenses are classified into the diffractive type. FineVision developed by PhysIOL has a 6.15 mm optical zone that serves as a diffractive zone, with an add power of +1.75D and +3.50D and an intermediate and near focal distance (theoretical value) of about 60 and 30 cm, respectively. AT LISA® tri 839 MP (Carl Zeiss Meditec AG) has a 6-mm optical zone that serves as a diffractive zone, with an add power of +1.66D and +3.33D and a focal distance (theoretical value) of about 80 and 40 cm, respectively. These two trifocal intraocular lenses have been reported to provide not only good distance and near, but also intermediate uncorrected visions 3) to 8). Neither of them has been approved in Japan.

The remaining one lens is TFNT00 developed by US Alcon (hereinafter called the investigational lens). It was given the CE mark in June 2015 and is now commercially available in EU. As with the Alcon® AcrySof® IQ ReSTOR® Single Piece of Alcon Japan (medical device approval number: 22000BZX00970000; hereinafter called SN6AD1) approved in Japan, the investigational lens provides multiple focuses based on the diffractive structure of the optical zone. SN6AD1 is a bifocal intraocular lens designed to have a diffractive zone with 3.6 mm around the optical part center, with an add power of +3D and a near focal distance (theoretical value) of about 40 cm. The investigational lens is designed to have a diffractive zone with 4.5 mm around the optical part center. This design change of the diffractive zone allows focusing on distance, intermediate, and near objects. The investigational lens has an add power of +2.17D and +3.25D and intermediate and near focal distances (theoretical value) of about 60 and 40 cm, respectively. It has an intermediate focus of 60 cm in addition to the distance and near (40 cm) focuses of SN6AD1. A non-clinical study (simulation with Badal images) performed to compare the visions potentially

achieved with the investigational lens and SN6AD1 showed that the investigational lens had a potential to provide equivalent distance and near visions to SN6AD1 and better intermediate visions at 80 and 60 cm^9). In general, diffractive lenses are structurally associated with diffraction loss and resulting reduced contrast sensitivity because not all the lights passing through the lens are focused on the retina. [REDACTED]

[REDACTED]

[REDACTED] A clinical study of SN6AD1 (C-07-44) showed an uncorrected distance VA (logMAR) of  $0.03 \pm 0.14$ , uncorrected near vision of  $0.04 \pm 0.12$ , and normal photopic contrast sensitivity for both distance and near visions at 1 year postoperation. Although these visual acuity values from Badal images were obtained from a simulation, the investigational lens can correct not only distance and near visions, but also an intermediate vision of about 60 cm and is therefore expected to contribute to the improved quality of vision after cataract surgery.

The present study (ILH297-C003) is intended to confirm the safety of the investigational lens and examine its effectiveness as a multifocal lens by examining the vision results at different distances and investigating the postoperative use of eyeglasses by subjects.

## (2) Summary of known and possible risks and benefits to subjects

Alcon has received the Approval to Market for TFNT00 with a CE mark in the European Union. But the results of clinical study have not been made available yet. In USA, a clinical study on this lens is in the planning stage. However, the plural clinical studies on same material IOLs were completed and in widespread clinical use in Japan and other countries. These clinical study data is described on investigator's brochure.

## 2. OBJECTIVE(S)

The objective of this study is to evaluate safety and effectiveness of AcrySof® IQ PanOptix™ IOL Model TFNT00 when implanted to replace the natural lens following cataract removal.

## 3. TEST ARTICLE(S)

### (1) Investigational lens

AcrySof® IQ PanOptix™ IOL Model TFNT00 (+3.25D and +2.17D add power)

#### Construction

Single-piece construction lens consisting of the optic and the haptic made of the same material, optic diameter: 6.0 mm, overall length: 13.0 mm [REDACTED]

[REDACTED] (See Fig.3-1)

[figure not shown]

Fig.3-1 Product Drawing (TFNT00)

#### Optic

Material: Cross-linked, acrylate/methacrylate copolymer with a chemically bonded ultraviolet and blue light absorber\*

\* : N-2-[3-(2-methylphenylazo)-4-hydroxyphenyl] ethyl methacrylamide [REDACTED]

Edge thickness: 0.21±0.05 mm

Add power: +3.25D, +2.17D

Refractive power: 12.5~26.5D (in 0.5 D increments)

### Haptic

Material: Same as the optic material

Shape: Modified-L

Angulation: 0°

### (2) Usage

The investigational lens will be placed within the capsular bag after removal of the natural crystalline lens following phacoemulsification. Bilateral implantation of the investigational lens is planned for all subjects. The lens is implanted first to the eye with more advanced cataract. If both eyes have a similar degree of cataract, perform the surgery first for the right eye. The time of surgery for the remaining eye (2nd eye) will be within 30days from the first surgery which will be decided by the investigators based on the results of the examination and observation at Visit 1 (1-2 days after 1st eye implantation).

#### [Justification for the intended use]

Since the investigational lens, like conventional IOLs, is a posterior chamber lens which is widely implanted following cataract extraction, phacoemulsification is adopted. To assess the binocular vision, the investigational lens will be implanted to bilateral eyes. Considering the safety of the study subjects, the time of implant to the remaining eye (2nd eye) will be decided based on the results of the 1st implant.

### (3) Instructions on package and labeling

Pack each investigational lens into the carton with labeling of:

- Name and address of the Sponsor
- Purpose (for use in clinical study)
- Lens model, serial number and refractive power, A-constant
- Method of storage and precautions

The package contains the following adhesive labels besides the investigational lens:

- Investigational lens control labels (to be attached to Investigational lens Control Log, medical record)
- Copy of the investigational lens information given to study subjects (to be attached to the Study Participants Card).

<Carton of the investigational lens>

(Side view)

Model:	Barcode	For Use of Clinical study	Illustration of the lens
Serial No	A-constant: ***.*		

(Front view)

Storage methods:

Keep the lens not at a high temperature/humidity and away from direct light.  
Do not keep the lens at 45°C or higher.

Precautions:

- This product is a sterilized product used only once. Do not re-sterilize or re-use the once opened product.
- Do not use the product if the package has a tear or if the package is opened and the sterility is not assured.

ALCON JAPAN LTD. [name]

<Adhesive label>

(Investigational lens Control Label)

For Use of Clinical study	Model: Refractive power: Serial No.:
---------------------------	--

(Copy of the investigational lens information given to study subjects)

Model:	Refractive power:
Name of study subject:	
Implant eye:	right / left
Overall length including the haptic:	
Optic diameter:	
Serial No.:	
Date of surgery:	
Surgeon:	

#### (4) Storage and Management

The investigational lens storage manager appointed at each study site appropriately stores and manages the investigational lens according to the investigational lens management operating procedure provided by Sponsor beforehand, and prepares the inventory on which the receipt and delivery of the product, such as use of the product by each investigator, are recorded.

### 4. SUBJECTS

#### (1) Estimated Total Sample Size

60 subjects 120 eyes

#### (2) Inclusion Criteria

The patient who meets all criteria specified in the following 1) through 9).

- 1) Adults, 20 years of age or older at the time of informed consent, of either gender, diagnosed with bilateral cataracts;
- 2) Able to comprehend and sign a statement of informed consent;
- 3) Willing and able to complete all required postoperative visits;
- 4) Calculated lens power within the available range;
- 5) Planned cataract removal by phacoemulsification;
- 6) Potential postoperative BCDVA of 0.5 decimal or better in both eyes;
- 7) Subject with preoperative astigmatism < 1.0 D  
Note: Corneal incisions made to reduce astigmatism will not be allowed during the course of the study.
- 8) Clear intraocular media other than cataract in both eyes;
- 9) The subject must be able to undergo second eye surgery within 30 days of the first eye surgery.

[Justification for the inclusion criteria]

1 and 5: Cataract extraction is the indication of the clinical study.

2 and 3: One of GCP requirements

4: Essential condition for implant of the investigational lens.

6, 7, 8 and 9: Conditions to minimize the potential non-IOL factors which may affect the visual acuity data

#### (3) Exclusion Criteria

[Exclusion Criteria Prior to Surgery]

The patient who meets any criteria specified in the following 1) through 21).

- 1) Significant irregular corneal aberration as demonstrated by corneal topography;
- 2) Inflammation or edema (swelling) of the cornea affecting post-operative visual acuity;
- 3) Subjects with diagnosed degenerative visual disorders (e.g. macular degeneration or other retinal disorders) that are predicted to cause future acuity losses to a level worse than 0.5 decimal for BCDVA;

- 4) Subjects who may be expected to require ocular surgery (other than blepharo-surgery, laser surgery of fundus and YAG capsulotomy) during the study;
- 5) Previous refractive surgery;
- 6) Amblyopia;
- 7) Clinically severe corneal dystrophy (eg., epithelial, stromal, or endothelial dystrophy), keratitis, keratoconjunctivitis, keratouveitis, keratopathy, or kerectasia;
- 8) Diabetic retinopathy;
- 9) Extremely shallow anterior chamber, not due to swollen cataract;
- 10) Microphthalmos;
- 11) Previous retinal detachment;
- 12) Previous corneal transplant;
- 13) Recurrent severe anterior or posterior segment inflammation of unknown etiology;
- 14) Rubella or traumatic cataract;
- 15) Iris neovascularization;
- 16) Glaucoma;
- 17) Aniridia;
- 18) Optic nerve atrophy;
- 19) Pregnancy;
- 20) Any subject currently participating in another investigational drug or device study.
- 21) Disqualified by the investigator or the sub-investigator because of physical or ophthalmic diseases

#### [Exclusion Criteria During Surgery]

The patient who meets any criteria specified in the following 1) through 8).

- 1) Mechanical or surgical manipulation required to enlarge the pupil; pupil size must be at least 4.5 mm or larger just prior to implantation;
- 2) Other planned ocular surgery procedures for the duration of the study;
- 3) Excessive iris mobility;
- 4) Significant vitreous loss;
- 5) Significant anterior chamber hyphema;
- 6) Uncontrollable intraocular pressure;
- 7) Zonular or capsular rupture or tear;
- 8) Bag-sulcus, sulcus-sulcus or unknown placement of the haptics.

In the event of zonular damage, capsulorhexis tear, or decentered capsulorhexis during surgery, the surgeon should decide whether the stability of the IOL would be compromised by the complication. If the IOL stability would be compromised, the study IOL should not be implanted, the subject should be discontinued from the study, and the surgeon should make arrangements to implant an alternative non-study IOL.

[Justifications for the exclusion criteria]

{Exclusion Criteria Prior to Surgery}

9, 12, 13, 17 and 20: Factors potentially affecting effectiveness evaluability and criteria to secure safety of study subjects

1, 2, 4, 5, 6, 7, 8, 11, 18 and 19: Factors potentially affecting effectiveness evaluability

3, 10, 14, 15, 16 and 21: Criteria to secure safety of study subjects

{Exclusion Criteria During Surgery}

1: Factors potentially affecting effectiveness evaluability

2-7: Criteria to secure safety of study subjects

## 5. STUDY DESIGN

Multi-center, single-arm and non-masked study

## 6. STUDY PROCEDURE

### (1) Outline

The investigational lens will be implanted to both eyes in subjects with bilateral cataract. Registration of patients and the implantation of the investigational lens will be conducted in consideration of securing 120 eyes in 60 subjects as the analysis subjects. As shown in (4) of this section, subjects will be followed for 120 to 180 postoperative of the second implant for effectiveness and safety evaluation of the investigational lens.

### (2) Eligibility Assessment and Subject Identification Code Allocation

Subjects are selected and subject code is assigned according to the following procedures.

1. After explanation of the content of study to subject, obtain consent to participate in the clinical study from the qualified subject. Subject code will be assigned after obtain consent.
2. Perform tests/observations (screening tests) necessary for the assessment according to the inclusion/exclusion criteria and the investigator will assess the qualification. In the case of meeting the exclusion criteria during surgery, do not implant the investigational lens to the eye and do not enroll the eye in the clinical study.
3. The same subject code will be used for both the first and second implants. Prior to the second implant, obtain consent to continuously participate in the clinical study from the subjects.

### (3) Surgical Technique

The lens is implanted first to the eye with more advanced cataract (1st eye). If both eyes have a similar degree of cataract, perform the surgery first for the right eye. The time of surgery for the remaining eye (2nd eye) will be within 30days from the first surgery which will be decided by the investigator based on the results of the examination and observation at Visit 1 (1-2 days after 1st eye implantation).

Each investigator should use his or her standard surgical technique on all subjects. A continuous tear capsulorhexis should be performed to open the anterior capsule. Implant of the investigational lens will follow

phacoemulsification. The investigational lens, including both haptics, should be placed within the capsular bag. If the standard surgical technique cannot be applied or if the investigational lens cannot be implanted, the subject should be discontinued from the study and an approved and marketed lens should be implanted instead of the investigational lens. All study subjects should receive the investigator's standard regimen of preoperative, operative, and postoperative medications.

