## 2) Surgery Day (Visit 00/00A)

Record surgical information at Visit 00 (1st eye) and Visit 00A (2nd eye) respectively, Obtain consent in continuation of the study from each subject prior to the surgery on the 2nd eye.

- Operative Eye

Indicate which eye is being implanted.

- Qualification during the surgery.

Assess qualification according to the inclusion/exclusion criteria during the surgery.

- Incision Site

Record the incision site (sclera, at limbus, or cornea).

- Anterior capsulorhexis Diameter

Indicate anterior capsulorhexis diameter (mm) to the nearest 0.1 mm.

- Final Incision Size

Indicate final incision size (mm) to the nearest 0.1 mm.

- Insertion Instrument

Indicate which approved instrument and cartridge was used to fold and insert the IOL through the wound.

- Problems during surgery

Indicate what problems, if any, occurred during surgery. If any exclusion criteria occur, discontinue the subject from the clinical study.

- Other procedures at this surgery

Any other procedures performed at this surgery should be indicated. Since other procedures at this surgery are included in the exclusion criteria, discontinue the subject from the clinical study.

- Ocular concomitant medications

Indicate the type of concomitant ocular medications (e.g. adrenocorticosteroid, chemotherapy, NSAIDs, IOP reducing drug) used during the surgery.

- Lens Information

Provide the IOL information (IOL model, refractive power, serial No.) also in the event of discontinuation of implant. Attach the adhesive label contained in the package of the investigational lens to the CRF and the Study Participants Card.

- Adverse events and Device deficiencies

[figure not shown]
Presence/absence of adverse events and device deficiencies are recorded.

[figure not shown]
[figure not shown]

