## 8. DISCONTINUED SUBJECTS

(1) Discontinued Subjects

The subject is discontinued in the following cases:

- 1) The investigational lens was removed for reasons of adverse events.
- 2) The investigator (or sub-investigator) judged it necessary to replace the investigational lens with another IOL.
- 3) The investigator (or sub-investigator) judged it necessary to discontinue the subject from the study.
- 4) The subject canceled the consent once issued.
- 5) The subject requested discontinuation of the study.
- 6) Continuation of the study was judged as impossible because of subject's referral or move during the study.
- 7) Other (discontinuation is necessary)

Upon discontinuation of the study, if the investigator or sub-investigator decided the examination or observation is necessary, the examination or observation should be carried out as far as possible under the subject's consent, and the date and reason of discontinuation are entered in the electric case report form. In case where continuation of the study is difficult because of discontinued visit of the subject to the clinic, the subject is followed over telephone, by mail or other appropriate means and the reason for discontinued visit, survival/death of the subject, presence/absence of adverse events, etc., are entered in the electric case report form.

If the investigational lens remained implanted in the subject after discontinuation of the study, the subject is informed as to the necessity of receiving periodical ophthalmological follow-up to assure safety at least 6 months after surgery, and the subject is asked to extent cooperation as much as possible.

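### If the second eye cannot be implanted, the whole subject is discontinued, so scheduled examination of the first eye, which keeps the study lens, generally ends by day 14

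*Protocol*

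**What the plan says.** Three places in the protocol discontinue the subject when one eye fails at surgery:

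- Section 6(3), Surgical Technique: "If the standard surgical technique cannot be applied or if the investigational lens cannot be implanted, the subject should be discontinued from the study".
- Section 4(3), Exclusion Criteria During Surgery, where a complication would compromise lens stability: "the study IOL should not be implanted, the subject should be discontinued from the study".
- Section 6(5)2), Surgery Day, which is headed for Visits 00 and 00A and so covers the second eye: "If any exclusion criteria occur, discontinue the subject from the clinical study".

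Section 6(2) is worded by eye: "do not implant the investigational lens to the eye and do not enroll the eye in the clinical study". It does not say what happens to a fellow eye that already has the lens.

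Section 8(1) also discontinues the subject after an explantation: "The investigational lens was removed for reasons of adverse events".

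On timing, section 6(3) says second-eye surgery "will be within 30days from the first surgery", and section 6(1) says "subjects will be followed for 120 to 180 postoperative of the second implant". The Summary likewise defines Visit 4A from second-eye implantation.

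The analysis sets are by eye. Section 9.1.2 puts every successfully implanted eye in the All-Implanted Analysis Set (AAS), and section 9.1.1 puts every eye with attempted implantation in the treatment-emergent safety set. Section 9.5 imputes nothing.

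**The concern.** The analysis sets follow the eye, but discontinuation follows the subject. A first eye with a successful implant belongs to both by-eye sets. If surgery on the other eye then fails, its scheduled examinations stop for a reason unrelated to its own lens.

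The study is meant to describe how the implanted lens performs and how safe it is. For an affected eye, the 120-180 day acuity, intraocular pressure, fundus and lens observations would be missing. Two Appendix B prompts to judge whether an adverse event has occurred could not arise at a scheduled visit: a pressure change of at least 10 mmHg after the first month, and corrected distance acuity worse than Visit 0 at Visit 4A.

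A site that followed section 6(2) and kept the first eye in the study would still have no second implantation date from which to set Visit 4A.

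**Working it through.** **The plan's own precision figure.** Protocol section 9.8 gives a half-width of 0.26 SD for n = 60. The formula is t(0.975, n-1)/√n, which gives 0.2583 at n = 60. The exact 95% interval for 30/60 comes out at 36.8% to 63.2%. Both stated figures reproduce.

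**Timing.** Inputs are the visit windows in the Summary and Table 6-1 (Visit 1 at days 1-2, Visit 2 at days 7-14, Visit 3 at days 30-60, Visit 4A at 120-180 days after the second implant) and second surgery by day 30 (section 6(3)). Let D be the day of second surgery on the first eye's clock, from 1 to 30.

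| D | First eye's last scheduled examination if the second implant fails |
|---|---|
| 1-6 | Visit 1 (days 1-2) |
| 7-14 | Visit 1 or Visit 2 |
| 15-29 | Visit 2 (days 7-14) |
| 30 | Visit 2, or Visit 3 if held that same day |

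Had the second implant succeeded, Visit 4A on the first eye's clock would fall at days 120+D to 180+D. That is 121-181 for D = 1 and 150-210 for D = 30, so 121-210 overall. The affected eye's scheduled examinations end by day 14 instead, apart from the day-30 case.

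**Explantation.** When a lens is removed, the fellow eye loses only the visits still to come, so the loss depends on when that happens.

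**How many eyes.** The documents give no rate of failed second implants. The range 1-5% is an assumption.

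- Expected eyes: 60 × 0.01 = 0.6; 60 × 0.05 = 3.0.
- Chance of at least one: 1 - 0.99^60 = 45.3%; 1 - 0.95^60 = 95.4%.

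**Precision if these subjects are not replaced.**

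| First eyes at the last visit | Half-width (SD) | Increase |
|---|---|---|
| 60 | 0.2583 | - |
| 59 | 0.2606 | 0.9% |
| 58 | 0.2629 | 1.8% |
| 57 | 0.2653 | 2.7% |

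With no events observed, the exact two-sided 95% upper limit, 1 - 0.025^(1/n), moves from 5.96% at n = 60 to 6.27% at n = 57.

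Section 6(1) plans enrolment "in consideration of securing 120 eyes in 60 subjects as the analysis subjects". If that allows replacement, precision is unchanged, but the late data on the retained lenses are still lost.

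**The case against.** The strongest reply is that the protocol foresaw a lens staying in place after discontinuation. Section 8(1) provides an examination where the investigator thinks one is needed, advice to have ophthalmological follow-up for at least 6 months after surgery, and contact by telephone or mail for subjects who stop attending. Section 10(5) recommends follow-up of unresolved adverse events. Until discontinuation, adverse events are recorded continuously and unscheduled visits are possible. These provisions largely answer the patient-care side. They do not answer the data side, because none is a scheduled study examination of the retained lens.

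Section 6(2) can be read as an eye-level rule, so the defect could be called unreconciled wording. That is partly right. But three places say subject, none says the first eye continues, and Visit 4A has no anchor on either reading.

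The two Appendix B prompts are not fully separate losses. The acuity prompt is made at Visit 4A, so it is part of the missed final visit. The pressure prompt is not tied to a particular visit and could still arise at one outside the schedule. What is lost is the Visit 3 and final examinations, plus Visit 2 when second surgery comes early.

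The study is bilateral by design, and ending participation when that condition fails is defensible. It makes no planned analysis invalid. The effect on precision is also slight: losing one or two eyes still rounds to the stated 0.26 SD. The shortfall would be visible in the N by visit and the disposition table. These points limit the weight of the concern but do not remove it.

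**Conclusion.** The concern holds and is minor. As written, a failed second implant ends scheduled examination of the first eye by day 14 in all but the day-30 case, while that eye stays in the primary effectiveness set and the safety set. The cost is late data on a few implanted lenses and, without replacement, a half-width up to 2.7% wider.

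The timing follows from the stated windows. The number of eyes rests on the assumed 1-5% failure rate, and the precision loss also rests on no replacement. The study has no hypothesis test or success criterion.

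**What to change.** Amend the protocol so that discontinuation from follow-up applies to the eye:

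1. Any eye still carrying the study lens completes its remaining scheduled examinations, with the subject's consent: Visit 2 if still due, Visit 3 and the 120-180 day visit.
2. When there is no second implant, count the 120-180 day visit from that eye's own surgery date.
3. These subjects have monocular tests only and stay out of the binocular tables.
4. Align sections 4(3), 6(2), 6(3), 6(5)2) and 8(1) with this rule.

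Optionally, extend the listings of missing follow-up in SAP 5.3.4 to 5.3.7 to the primary acuity variables, unless redacted SAP text already does so.

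The cost is a short amendment with written agreement and IRB review as needed under section 12, plus two or three retained visits per affected subject. At the assumed 1-5% that is between 0.6 × 2 = 1.2 and 3 × 3 = 9 visits, all using examinations already planned.
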